5.2 Baseline Definitions

For all endpoints (except as noted in baseline definitions) the baseline value will be the latest pre-dose assessment, including those from unscheduled visits. If time is not collected, Day 1 assessments are assumed to be taken prior to first dose and used as baseline. In part 1, baseline definitions are applicable to each period.

Parameter	Study Assessments Considered As Baseline				Baseline Used in
	Screening	Day -2	Day -1	Day 1 (Pre-Dose)	Data Display
Safety Data		•		•	
Vital Signs	Х	X*	X	X	Mean of replicate assessments on Day
ECG	Х	X*	Х	X	Mean of replicate assessments on Day
Laboratory tests	Х	X*	Х		Day -1

^{*} Vital Sign, ECG and laboratory tests are not collected at day -2 for Part 2.

Unless otherwise stated, if baseline data is missing no derivation will be performed and baseline will be set to missing.

5.3 Multicentre Studies

Not applicable.

5.4 Examination of Covariates, Other Strata and Subgroups

Not applicable.

5.5 Multiple Comparisons and Multiplicity

Not applicable.

5.6 Other Considerations for Data Analyses and Data Handling Conventions

Other considerations for data analyses and data handling conventions are outlined in the appendices:

Section	Component
14.3	Appendix 3: Assessment Windows
14.4	Appendix 4: Study Phases and Treatment Emergent Adverse Events
14.5	Appendix 5: Data Display Standards & Handling Conventions
14.6	Appendix 6: Derived and Transformed Data
14.7	Appendix 7: Reporting Standards for Missing Data

Section	Component
14.8	Appendix 8: Values of Potential Clinical Importance

6. STUDY POPULATION ANALYSES

6.1 Overview of Planned Analyses

The study population analyses will be based on the Safety Population, unless otherwise specified.

Study population analyses including analyses of participant's disposition, protocol deviations, demographic and baseline characteristics, prior and concomitant medications, and exposure and treatment compliance will be based on GSK Core Data Standards. Details of the planned displays are presented in Appendix 12: List of Data Displays.

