10.2. Populations for Analyses

For purposes of analysis, the following populations are defined:

All Participants Screened Population

The All Participants Screened Population will include all participants who consent to participate in the clinical study. Participants in this population will be used for disposition summary.

Safety Population

The Safety Population will include all participants who received at least 1 dose of the study treatment (including placebo) with at least 1 post-baseline safety assessment. Participants in this population will be used for all demographic and safety summaries or listings. The population will be defined separately for Part 1A, Part 1B and Part 2 of the study.

Pharmacokinetic Population

The PK Population will include all participants in the Safety population for whom at least one evaluable PK sample is obtained and analyzed. Pharmacokinetic samples that may be affected by protocol deviations will be reviewed by the study team to determine whether or not the sample will be excluded. All PK analyses will be based on this analysis population. The population will be defined separately for Part 1A, Part 1B, and Part 2 of the study.

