10.4. Statistical Analyses

All safety analyses will be performed on the Safety Population.

All PK analyses will be performed on the PK Population.

For assessment of relative bioavailability of tablet versus capsule (AUC($0-\infty$) and Cmax) and effect of food (AUC($0-\infty$), Cmax, and tmax), loge-transformed selected PK parameters (except tmax) will be analyzed using a mixed effects model. The point estimates and their associated 90% confidence interval (CI) will be provided for the

ratios, test/reference (for bioavailability) and fed/fasted (food effect) in PK parameter values on the original scale.

For the parameter tmax, the corresponding non-parametric analysis will be performed on the original scale using CIs for the estimation of the treatment difference.

Steady-state GSK2838232 concentrations will be assessed by estimating the slope of predose concentrations following repeated daily administration. Accumulation of plasma GSK2838232 will be assessed as the ratios of Day 11/Day 1 AUC(0- τ), Cmax, and C τ values.

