2. SUMMARY OF KEY PROTOCOL INFORMATION

2.1 Changes to the Protocol Defined Statistical Analysis Plan

There were no changes or deviations to the originally planned statistical analysis specified in the amended protocol (dated: 17-JUL-2017).

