4. ANALYSIS POPULATIONS

Population	Definition / Criteria	Analyses Evaluated
Screened	All participants who were screened for eligibility	 Study Population
Safety	 The Safety Population will include all participants who received at least 1 dose of the study treatment (including placebo) with at least 1 post-baseline safety assessment. This population will be based on the treatment the participant received. The population will be defined separately for Part 1 and Part 2 of the study. 	Safety and Demography

Population	Definition / Criteria	Analyses Evaluated
PK	 All participants in the Safety population who had at least 1 non-missing PK assessment (Non-quantifiable [NQ] values will be considered as non-missing values). Pharmacokinetic samples that may be affected by protocol deviations will be reviewed by the study team to determine whether the sample will be excluded. This population will be based on the treatment the participant received. The population will be defined separately for Part 1A, Part 1B and Part 2 of the study. 	• PK

NOTES:

 Please refer to Appendix 8: List of Data Displays which details the population to be used for each displays being generated.

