14.6.2 Study Population

Demographics

Age

- GSK standard IDSL algorithms will be used for calculating age where birth date will be imputed as follows:
 - Any participant with a missing day will have this imputed as day '15'.
 - Any participant with a missing date and month will have this imputed as '30th June'.
 - The age will be calculated by Data Management and mapped from ClinBase to SDTM dataset DM
- Birth date will be presented in listings as 'YYYY'.

Body Mass Index (BMI)

Calculated as Weight (kg) / [Height (m)]²

Treatment Compliance

Treatment compliance will be calculated based on the formula:

Treatment Compliance = Number of Actual Doses / (Planned Treatment Duration in Days * Frequency)

- Frequency is 2 for BID and 1 for QD. Treatment compliance could be greater than 100% if there are events of overdose. Cumulative compliance (since Day 1) at each visit will be calculated.
- Planned Treatment Duration is defined as 1 day for study part 1, and as 11 day for study part 2.

Extent of Exposure

- Number of days of exposure to study drug will be calculated based on the formula:
 Duration of Exposure in Days = Treatment Stop Date (Treatment Start Date) + 1
- Participants who were randomized but did not report a treatment start date will be categorised

Demographics

as having zero days of exposure.

• The cumulative dose will be based on the formula:

Cumulative Dose = Sum of (Number of Days x Total Daily Dose)

• If there are any treatment breaks during the study, exposure data will be adjusted accordingly.

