14.12.4 Study Population Tables

Study I	Study Population Tables						
No.	Population	IDSL / Example Shell	Title	Programming Notes	Deliverable [Priority]		
Particip	ant Disposition	n					
1.1.	Safety	ES8	Summary of Participant Status and Reason for Study Withdrawal – Part 1	ICH E3, FDAAA, EudraCT Summarize by treatment /sequence and overall of each part	SAC [1]		
1.2.	Safety	ES8	Summary of Participant Status and Reason for Study Withdrawal – Part 2	ICH E3, FDAAA, EudraCT Summarize by treatment /sequence and overall of each part	SAC [1]		
1.3.	Safety	SD1	Summary of Treatment Status and Reasons for Discontinuation of Study Treatment – Part 1	ICH E3 Summarize by treatment /sequence and overall of each part	SAC [1]		
1.4.	Safety	SD1	Summary of Treatment Status and Reasons for Discontinuation of Study Treatment – Part 2	ICH E3 Summarize by treatment /sequence and overall of each part	SAC [1]		
1.5.	Safety	ES4	Summary of Participant Disposition at Each Study Epoch – Part 1	ICH E3	SAC [1]		
1.6.	Safety	ES4	Summary of Participant Disposition at Each Study Epoch – Part 2	ICH E3	SAC [1]		
1.7.	Screened	ES6	Summary of Screening Status and Reasons for Screen Failure – Part 1	Journal Requirements	SAC [1]		
1.8.	Screened	ES6	Summary of Screening Status and Reasons for Screen Failure – Part 2	Journal Requirements	SAC [1]		

Study F	Study Population Tables						
No.	Population	IDSL / Example Shell	Title	Programming Notes	Deliverable [Priority]		
Protoco	ol Deviation						
1.9.	Safety	DV1	Summary of Protocol Deviations – Part 1	ICH E3	SAC [1]		
1.10.	Safety	DV1	Summary of Protocol Deviations – Part 2	ICH E3	SAC [1]		
Popula	tion Analysed						
1.11.	Screened	SP1	Summary of Study Populations – Part 1	By treatment and combined overall	SAC [1]		
1.12.	Screened	SP1	Summary of Study Populations – Part 2	By treatment and combined overall	SAC [1]		
Demog	raphic and Bas	eline Characteris	tics				
1.13.	Safety	DM3	Summary of Demographic Characteristics – Part 1	ICH E3, FDAAA, EudraCT	SAC [1]		
1.14.	Safety	DM1	Summary of Demographic Characteristics – Part 2	ICH E3, FDAAA, EudraCT	SAC [1]		
1.15.	Safety	DM11	Summary of Age Ranges – Part 1	EudraCT	SAC [1]		
1.16.	Safety	DM11	Summary of Age Ranges – Part 2	EudraCT	SAC [1]		
1.17.	Safety	DM5	Summary of Race and Racial Combinations – Part 1	ICH E3, FDA, FDAAA, EudraCT	SAC [1]		
1.18.	Safety	DM5	Summary of Race and Racial Combinations – Part 2	ICH E3, FDA, FDAAA, EudraCT	SAC [1]		
Prior ar	Prior and Concomitant Medications						

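### Disposition, withdrawal and exclusion displays are set on the Safety Population, so they cannot report a randomised participant who falls outside it; the protocol assigns disposition to the Screened Population

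*SAP*

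**What the plan says.** Protocol 10.2 defines the All Participants Screened Population as everyone who consents and adds: "Participants in this population will be used for disposition summary". It limits the Safety Population to "all participants who received at least 1 dose of the study treatment (including placebo) with at least 1 post-baseline safety assessment". Protocol 10.4 states: "All safety analyses will be performed on the Safety Population". Protocol 10.4.1, under Safety Analyses, includes the number and percentage withdrawing from treatment or study, with reasons.

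SAP 4 keeps the same two-part Safety rule ("received at least 1 dose of the study treatment (including placebo) with at least 1 post-baseline safety assessment") and lists Screened as the population for Study Population analyses. SAP 6.1 then sets a different default for those analyses and names disposition among them: "The study population analyses will be based on the Safety Population, unless otherwise specified".

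The SAP list of displays (14.12.4 and 14.12.17) follows that default. Tables 1.1-1.6, beginning with "Summary of Participant Status and Reason for Study Withdrawal – Part 1", are on Safety. So are Listings 3-6 (study withdrawal, treatment discontinuation) and Listings 14-15 (participants excluded from any population). Tables 1.7-1.8 and 1.11-1.12 and Listings 1-2 are on Screened. The SAP Addendum leaves these populations as they are. SAP 2.1 states: "There were no changes or deviations to the originally planned statistical analysis specified in the amended protocol".

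**The concern.** A disposition table should account for everyone randomised, and a list of exclusions should name the people excluded. Under the Safety flag, a participant who leaves after randomisation but before a dose, or after a dose but before any post-baseline safety assessment, is removed from both numerator and denominator of the withdrawal tables. The reason for leaving appears in no planned disposition table or withdrawal listing. With 16 and 10 participants planned, losing one person visibly changes a percentage, and the loss can only lower the displayed withdrawal rate. The departure from the protocol's disposition population is also undeclared.

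**Working it through.** **Step 1: population by display.**

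| Display | Content | SAP population | Protocol basis |
|---|---|---|---|
| Tables 1.1-1.4, Listings 3-6 | Study withdrawal, treatment discontinuation | Safety | Unclear: 10.2 gives disposition to Screened; 10.4 and 10.4.1 put withdrawal on Safety |
| Tables 1.5-1.6 | Disposition by study epoch | Safety | Screened (10.2) |
| Tables 1.7-1.8, Listings 1-2 | Screening status, screen failure | Screened | Screened |
| Tables 1.11-1.12 | Counts in each population | Screened | No conflict |
| Listings 14-15 | Participants excluded from any population | Safety | Not specified; SAP 6.2 promises the listing |
| Tables 1.23-1.24 | Exposure | Safety | Not specified |

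Six of the eight tables under Participant Disposition are on Safety and two on Screened.

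**Step 2: who is lost.** Take a randomised participant who lacks a dose or lacks a post-baseline safety assessment.

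- They are not in Safety, so they are absent from Tables 1.1-1.6 and Listings 3-6.
- Tables 1.7-1.8 may count them as screened, and Tables 1.11-1.12 may show them as a gap between populations. Neither gives a withdrawal reason. They are not screen failures, since Protocol 6.4 reserves that term for people who were not randomised.
- Listings 14-15 can show someone in Safety who is excluded from the PK Population. They cannot show someone excluded from Safety, because that person is not in the listing's own population.
- SAP 14.6.2 has a rule for this group: "Participants who were randomized but did not report a treatment start date will be categorised" as having zero days of exposure. Someone never dosed cannot be in Safety, so the rule cannot operate in Tables 1.23-1.24.

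**Step 3: the plan's drop-out figure.** Protocol 10.1 allows for 25% drop-out.

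- Part 1: 12/(1 − 0.25) = 16, as stated.
- Part 2: 8/(1 − 0.25) = 10.67, rounded up to 11, against 10 stated. Multiplying instead gives 8 × 1.25 = 10. The difference does not affect this point.

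**Step 4: illustration of size.** Let N be randomised, w withdrawals, and k the withdrawals that fall outside Safety. The all-randomised rate is w/N and the Safety-based rate is (w − k)/(N − k). The documents give no value for k, so 0, 1 and 2 are assumed. For w, the gap between enrolled and evaluable is used: 16 − 12 = 4 and 10 − 8 = 2.

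| | All randomised | k = 0 | k = 1 | k = 2 |
|---|---|---|---|---|
| Part 1 | 4/16 = 25.0% | 4/16 = 25.0% | 3/15 = 20.0% | 2/14 = 14.3% |
| Part 2 | 2/10 = 20.0% | 2/10 = 20.0% | 1/9 = 11.1% | 0/8 = 0% |

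**The case against.** The strongest defence is that the SAP follows the protocol. Protocol 10.4.1 lists withdrawal summaries among the safety analyses, and 10.4 puts all of those on Safety. The Screened sentence in 10.2 could then be met by Tables 1.7-1.8 and 1.11-1.12. For Tables 1.1-1.4 and Listings 3-6 this has force: the protocol is inconsistent, and SAP 2.1 cannot be called plainly wrong about them. It does not cover Tables 1.5-1.6, which are disposition summaries by title, or Listings 14-15. SAP 14.7.2 also promises that exclusions from summaries will be documented in the study report. That is a useful safeguard, but no planned display delivers it for people outside Safety.

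A reader might also infer several stronger things that the documents do not support:

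- *That all early leavers vanish from every disposition display.* Some displays are on Screened, and anyone with a dose and a post-baseline safety assessment stays in Safety. Dosing is supervised on site, and vital signs and ECG follow 1 hour after GSK2838232, so few dosed participants would be lost.
- *That the SAP departs from the protocol on adverse events.* Both documents use the same population and the same post-baseline condition. AEs are collected only from the start of treatment, and a dosed participant with a recorded on-treatment AE would ordinarily have had a post-dose safety assessment.
- *That anyone withdrawn during the Period 1 ritonavir run-in is outside Safety.* Ritonavir counts as study treatment (Protocol 7). Protocol 10.3 puts baseline before the first dose of study treatment, so Day -1 assessments may be post-baseline. SAP 5.2 puts baseline at Day -1 or Day 1 pre-dose. Membership depends on which rule governs, and SAP 5.2 does not say that it governs population membership.
- *That a fall from 25.0% to 14.3% is to be expected.* Nothing supports two of four drop-outs leaving before any assessment; at k = 0 the effect is nil.

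**Conclusion.** The point holds in a limited form. There is an undeclared conflict with Protocol 10.2, clear for Tables 1.5-1.6 and blurred by the protocol's own inconsistency for Tables 1.1-1.4 and Listings 3-6. Independently of that conflict, the withdrawal displays cannot give a reason for a randomised participant outside Safety, Listings 14-15 cannot show such a person, and the zero-exposure rule cannot operate.

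The number affected is probably small and may be zero. The figures of 20.0% and 14.3% against 25.0% in Part 1, and 11.1% and 0% against 20.0% in Part 2, rest on assumed values of w and k; they show sensitivity in small cohorts and are not a forecast. The pharmacokinetic estimates are not at issue here. The correction is worth making because it costs almost nothing and lets these displays report the people they exist to report.

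**What to change.** 1. In SAP 4, define an all-randomised set as a subset of Screened.
2. Change the population flag to that set for Tables 1.1-1.6 and Listings 3-6 and 14-15.
3. In SAP 2.1, record the choice and how it reconciles Protocol 10.2 with 10.4.1.
4. For the zero-exposure rule in SAP 14.6.2, either apply it in a display that includes undosed randomised participants or delete it.
5. Optionally, define Safety in both documents as everyone who received any dose of study treatment, and require a post-baseline value only in change-from-baseline displays. This improves a definition that the protocol and SAP share; it does not correct a SAP departure. It would still leave out a randomised participant who was never dosed, so it does not replace steps 1 and 2.

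The cost is one added definition, some changed population flags and a few sentences, plus one protocol sentence if step 5 is taken. The downside is that some denominators may include a participant with very few data.

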6.2 Disposition of Participants

A summary of the number of participants in each of the analysis populations described in Section 4 will be provided and this table will be displayed by treatment/sequence and overall of each part. A listing of participants excluded from analysis populations will also be provided.

A summary of participant status and reason for study withdrawal will be provided. This display will show the number and percentage of participants who withdrew from the study, including primary reasons for study withdrawal.

A summary of study treatment status will be provided. This display will show the number and percentage of participants who have completed the study or have discontinued study treatment and a summary of the primary reasons for discontinuation of study treatment. A listing of study treatment discontinuation will be generated. The listing will include last dose date, and reasons for study treatment discontinuation as well as study part and period, when applicable, of discontinuation.

6.3 Demographic and Baseline Characteristics

The demographic characteristics (e.g., age, ethnicity, sex, height, and body weight) will be summarized and listed by participant. Race will be summarized and listed separately from the other demographic characteristics. Age, height, body mass index (BMI) and weight will be summarized using the mean, standard deviation, minimum, median, and maximum. The count and percentage will be computed for sex, race and ethnicity. The summary table will be displayed by treatment/treatment sequence and overall of each part.

Medical conditions present at screening will be summarized by treatment/treatment sequence and overall of each part, and listed by participant.

Substance use will be listed.

6.4 Concomitant Medications

Concomitant medications will be coded using GSK Drug coding dictionary, summarized by treatment and study part, and listed by participant. The summary of concomitant

medications will show the number and percentage of participants taking concomitant medications by ingredient. Multi-ingredient products will be summarized by their separate ingredients rather than as a combination of ingredients. Anatomical Therapeutic Chemical (ATC) classification Level 1 (Body System) information will be included in the dataset created, however, will not appear on the listing or summary.

In the summary of concomitant medications, each participant is counted once within each unique ingredient. For example, if a participant takes amoxicillin on two separate occasions, the participant is counted only once under the ingredient "amoxicillin".

In the summary of concomitant medications, the ingredients will be summarized by the base only, using CMBASECD and CMBASE.

6.5 Treatment Compliance and Protocol Deviations

Information of each participant not received the correct treatment during each treatment period, the reason for not receiving the correct treatment, and any other protocol deviations will be summarized by treatment /sequence and overall of each part, and listed by participant and period (treatment). In addition, a listing will be provided including dose administered along with dosing dates and time for the investigational product.

Participants who did not satisfy all inclusion and exclusion criteria and corresponding criteria that were violated will be summarized and listed.

For the food effect of Part 1, a by-participant listing of the meal data will also be generated including start and stop date and time of meal, dosing time, type of meal and whether the totality of the meal was ingested.

6.6 Extent of Exposure

A by-participant summary of treatments administered in each part will be generated, with dose, and dosing start date, dosing end date and number of dose. A by-participant listing of data on participant exposure will be generated including dose date and time, unit, formulation, route and frequency.

7. EFFICACY ANALYSES

Not applicable.

8. SAFETY ANALYSES

The safety analyses will be based on the "Safety Population", unless otherwise specified.

8.1 Adverse Events Analyses

Adverse events analyses including the analysis of adverse events (AEs), Serious (SAEs) and other significant AEs will be based on GSK Core Data Standards. The details of the planned displays are provided in Appendix 12: List of Data Displays.

8.2 Adverse Events of Special Interest Analyses

Not applicable.

8.3 Clinical Laboratory Analyses

Laboratory evaluations including the analyses of Chemistry laboratory tests, Hematology laboratory tests, Urinalysis, and liver function tests will be based on GSK Core Data Standards. The details of the planned displays are in Appendix 12: List of Data Displays.

8.4 Other Safety Analyses

The analyses of non-laboratory safety test results including ECGs and vital signs will be based on GSK Core Data Standards, unless otherwise specified. The details of the planned displays are presented in Appendix 12: List of Data Displays.

9. PHARMACOKINETIC ANALYSES

9.1 Primary Pharmacokinetic Analyses

9.1.1 Endpoint / Variables

9.1.1.1 Drug Concentration Measures

Pharmacokinetic data will be presented in graphical and/or tabular form and will be summarized descriptively. Plasma GSK2838232 concentration-time data will be listed by participant, treatment group and time and summarized by treatment group and time for each part of the study. Individual participant profiles for GSK2838232 concentration-time data will be presented on both a linear and semi-log scale. Linear and semi-log figures for mean and median GSK2838232 plasma concentrations versus time will also be generated.

Refer to Appendix 5: Data Display Standards & Handling Conventions (Section 14.5.3 Reporting Standards for Pharmacokinetic).

